3.1.1 Recruitment and Screening Phase

Candidate subjects will be informed of this study as per mechanisms described in **Section 4.3**, **Subject Recruitment**.

Subjects must meet all inclusion criteria and not violate any exclusion criteria to enroll into this study. Signed informed consent will be obtained from all subjects or their legally authorized representative (LAR), as appropriate, prior to the performance of any protocol-specific activities. The licensed site investigator or his or her designee will obtain consent from subjects at their respective sites. After signing the informed consent, subjects will be considered to be enrolled in the study. All subjects who have signed an informed consent for participation in the study will be assigned a Global Unique Identifier (GUID) using the National Institutes of Health Subjects Global Rare Disease Registry GUID tool available at https://grdr-quid.ncats.nih.gov. Once consented, subjects will undergo a Screening and Baseline (Visit 1, **Section 6.1.1, Baseline Visit**) including pregnancy testing of female subjects of childbearing potential. The licensed site investigator or designated staff member will complete a Patient Evaluation Form confirming all inclusion criteria are met and no exclusion criteria are violated. The Lead Principal Investigator will confirm the subject's eligibility. Subjects whose eligibility is confirmed will continue to the Intervention Phase; those found to violate any criteria will be considered screening failures.

3.1.2 Intervention Phase

Adult subjects will receive an oral sirolimus loading dose of 5 mg/m², rounded to the nearest mg (day 1). Loading dose may be lower at the discretion of the prescribing physician. Starting on day 2, adult subjects will receive oral sirolimus daily at 2.5 mg/m²/day (rounded to the nearest mg), adjusted as needed to a target trough level of 10-15 ng/mL. Pediatric subjects will not receive a loading dose, and daily dosing will be at 2 mg/m²/day (rounded to the nearest mg), adjusted to achieve a target trough level of 5-15 ng/mL. Subjects will remain on treatment for 12 ± 1 month. The period between the loading dose/first dose and the last treatment define the "Intervention Phase". Patients will continue to receive standard of care treatment during the Intervention Phase consistent with the requirements of **Section 6.6, Subject Withdrawal**. Subjects will undergo regular Intervention Phase visits (**Section 6.2, Intervention Phase**). The licensed site investigator will be ultimately responsible for all treatment decisions, including when to initiate rescue therapy (**Section 6.4, Rescue Therapy**).

3.1.3 Follow Up Phase

Subjects will be contacted via telephone 12 ± 2 weeks following the End of Treatment Visit or Early Termination Visit to document changes in health, medications and to monitor for pregnancy.

3.1.4 Allocation to Interventional Group

All subjects will receive drug; no randomization will occur.

3.2 Study Endpoints

3.2.1 Primary Study Endpoints

The primary endpoint of this study will be the proportion of patients achieving a positive CBR response (**Section 7.6**, **Efficacy Evaluations**) at 12 ± 1 month. Assessments at 12 ± 1 month will be compared to those obtained at the Baseline Visit.

3.2.2 Secondary Study Endpoints

The secondary endpoints of this study will be:

- The proportion of patients achieving a positive CBR response (**Section 7.6**, **Efficacy Evaluations**) at 3, 6, and 9 months ± 2 weeks following administration of sirolimus loading dose. Assessments will be compared to those obtained at the Baseline Visit.
- The proportion of patients that remain on study drug for the duration of the study.
- The proportion of patients that indicate that they are currently receiving sirolimus at the end of the Follow Up Phase.
- Disease activity, as measured by the CHAP scale, at 3, 6, and 9 months ± 2 weeks and 12 ± 1 month. Assessments will be compared to those obtained at the Baseline Visit.
- Disease activity, as measured by MCD-related Overall Symptom Score as measured by 34 outcome measures (Section 7.6, Efficacy Evaluations), at 3, 6, and 9 months ± 2 weeks and 12 ± 1 month. Assessments will be compared to those obtained at the Baseline Visit.
- The proportion of patients achieving a lymph node response, following the modified Cheson response criteria (**Section 7.6, Efficacy Evaluations**). Assessments will be compared to those obtained at the Baseline Visit.

3.2.3 Exploratory Study Endpoints

The exploratory endpoints of this study will be:

- Results of correlative studies, in the research laboratory, to investigate the mechanism of action of sirolimus in iMCD and clinical and laboratory biomarkers for treatment response.
 Additional correlative findings may also be assessed.
- Spleen size, as measured by PET/CT or CT.

3.2.4 Safety Endpoints

The safety of sirolimus administration will be evaluated by monitoring for by:

- All previously reported adverse events (AEs) associated with sirolimus treatment
- All possible new AEs

4 Study Population and Duration of Participation

4.1 Inclusion Criteria

To be eligible, subjects must meet all of the below inclusion criteria:

- 1. Male or female, age 2-80
- Documented disease history consistent with the diagnostic criteria for iMCD (Appendix 15.1)
 - Confirmation of clinico-histopathological features by licensed pathologist, or a CAS grade of at least 3 in the companion registry study (ACCELERATE)
- 3. Failed/refractory (patient did not achieve sufficient disease control with anti-IL-6 therapy, as determined by the site investigator), relapsed (return of symptoms while on therapy), or inability to tolerate anti-IL-6 or anti-IL-6 receptor therapy
- 4. Evidence of active disease, defined as at least two abnormalities in the criteria comprising the CBR criteria and as defined as abnormal by CTCAE v4.0, including at least one objective measurement (hemoglobin, weight loss, or lymph node size)
 - Hemoglobin < lower limit of normal
 - Fatigue, including fatigue relieved by rest
 - Anorexia, including loss of appetite without alteration in eating habits
 - Fever or night sweats
 - Weight loss ≥ 5% from baseline
 - At least one lymph node meeting modified Cheson criteria (**Appendix 15.2**)
- 5. Ability to consume oral medication in the form of a tablet
- 6. Ability to provide, or for a LAR to provide on their behalf, informed consent prior to any study-specific activities

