7.6 Efficacy Evaluations

The below measures will be used to assess the efficacy of the study intervention and determine if the subject meets criteria for a CBR. All comparisons are against those obtained during the Baseline Visit:

Positive response: Relative to baseline, improvement in at least one of the below criterion without worsening of any single criterion other than hemoglobin on two consecutive study visits.

Negative response: Relative to baseline, worsening of any single criterion other than hemoglobin on two consecutive site visits or failure to achieve improvement for any criterion.

	Hemoglobin	Fatigue	Anorexia	Fever and night sweats	Weight	Lymph node size
Improvement	≥2 g/dL increase without transfusions	≥1 grade decrease by NCI CTCAE version 4.0, May, 2009	≥1 grade decrease by NCI CTCAE version 4.0, May, 2009	≥2°C decrease in fever or return to normal body temperature (37°C) or improvement in night sweats, as assessed by licensed site investigator	≥5% increase not due to increase in new or existing edema	≥25% decrease bi-dimensionally in size of largest lymph node, as measured using Cheson criteria (Appendix 15.2)
Worsening		≥2 grade increase by NCI CTCAE version 4.0, May, 2009	≥2 grade increase by NCI CTCAE version 4.0, May, 2009	≥2°C increase in fever or worsening in night sweats, as assessed by licensed site investigator	≥5% decrease (weight loss not due to decreased edema)	≥25% increase bidimensionally in size of largest lymph node, as measured using Cheson criteria (Appendix 15.2)

The below table provides the CHAP score, which will be used to assess the efficacy of the study intervention. All comparisons are against those obtained during the Baseline Visit:

Score:	0	1	2	3	4
CRP (mg/dL)	<1	≥1, <5	≥5, <10	≥10, <20	≥20
Hemoglobin (g/dL)	≥12	<12, ≥10	<10,≥8	<8	Transfusion dependent
Albumin (g/dL)	≥3	<3,≥2.5	<2.5, ≥2	<2, ≥1.5	<1.5
Performance Score (ECOG)	0	1	2	3	4

The below table provides the modified Cheson response criteria, which will be used to assess the efficacy of the study intervention. Unless otherwise specified, all comparisons are against those obtained during the Baseline Visit:

Complete Response (CR)	All index lesion(s) must have regressed to normal size (≤1.0 cm in		
	their greatest transverse diameter. No new sites of		
	lymphadenopathy >1.5 cm in longest dimension.		
Partial Response (PR)	≥50% decrease in sum of the products of the greatest diameters		

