	(SPD) of index lesion(s), and no new sites of lymphadenopathy >1.5		
	cm in longest dimension.		
Stable Disease (SD)	Failure to achieve a CR or PR (see above) without evidence of		
	progressive disease (see below).		
Progressive Disease (PD)	≥50% increase from nadir in the SPD of any index lesion, or		
	appearance of any new sites of lymphadenopathy that measure >1.5		
	cm in longest dimension during or at the end of therapy.		

MCD-related Overall Symptom Score: In addition to the defined CBR, 34 measures of disease activity will be prospectively evaluated and graded (as per CTCAE version 4.0, May, 2009), which will be used to assess the efficacy of the study intervention. All comparisons are against those obtained during the Baseline Visit:

General MCD-related

- Fatigue
- Malaise
- Hyperhidrosis
- Night sweats
- Fever
- Weight loss
- Anorexia
- Tumor pain
- Dyspnea
- Pruritis

Autoimmune phenomena

- Autoimmune disorder
- Immune system disorder

Fluid retention

- Generalized edema
- Edema face
- Edema limbs
- Edema trunk
- Genital edema
- Localized edema
- Neck edema
- Periorbital edema
- Capillary leak syndrome

- Ascites
- Pleural effusion
- Pericardial effusion

Neuropathy

- Peripheral motor neuropathy
- Peripheral sensory neuropathy
- Nervous system disorder, other

Skin disorders

- Rash acneiform
- Rash maculo-papular
- Papulopustular rash
- Purpura
- Skin hyperpigmentation
- Skin induration
- Skin disorder, other

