8.6 Subject Population(s) for Analysis

Any subject enrolled into the study that receives at least one dose of investigational product will be included for all analyses for each Visit they complete.

9 Safety and Adverse Events

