15.2 Modified Cheson Criteria

Lymph node selection: Up to six dominant lymph nodes ("index lesions") should be selected according to the following features:

- they should be clearly measurable in at least two perpendicular dimensions, ≥1.0 cm in the long axis, and ≥1.0 cm in the longest perpendicular transverse dimension to the long axis
- they should be from as disparate regions of the body as possible and chosen such that they are representative of the subject's disease
- they should include mediastinal and retroperitoneal areas of disease whenever these sites are involved

Lymph node measurement: The long axis and the longest perpendicular transverse dimension to the long axis of each lymph node should be measured (together, the greatest diameters).

Calculating lymph node response:

CBR response criteria: The largest of the index lesions selected at baseline should be analyzed to determine CBR response.

Positive Response: ≥25% decrease in the product of the greatest diameters, as compared to the same lymph node at baseline.

Negative Response: ≥25% increase in the product of the greatest diameters, as compared to the same lymph node at baseline.

Example: If at baseline, the long axis = 3.0 cm and the longest perpendicular transverse dimension = 2.0 cm, then the baseline value calculated for this node would be 6.0. To achieve a positive response, the node would have the shrink so that that product of the two measurements is ≤ 4.5 . (e.g. 2 cm x 2.25 cm).

Cheson response criteria: all index lesions should be considered. When determining response, nodal measurements should be calculated independently and as the sum of the product of the greatest diameters, as described in (**Section 7.6 Efficacy Evaluations**).

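### Subjects with no baseline index lesion can enter, and sections 7.6 and 8.6 read together count them as non-responders in the secondary nodal response proportion

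*Combined protocol and SAP*

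**What the plan says.** - **Entry.** Inclusion 4 (section 4.1) lists six CBR-based abnormalities and needs two, "including at least one objective measurement (hemoglobin, weight loss, or lymph node size"). The nodal item, "At least one lymph node meeting modified Cheson criteria", is one of the six and is not mandatory.
- **Diagnosis.** Inclusion 2 asks for "Documented disease history consistent with the diagnostic criteria for iMCD". Appendix 15.1 makes enlarged nodes in two or more stations a major diagnostic criterion, but inclusion 2 is met by history and does not require a node at study baseline.
- **Endpoint.** Section 3.2.2 lists "The proportion of patients achieving a lymph node response, following the modified Cheson response criteria". It does not restrict this to subjects who had a node to follow.
- **Response categories.** In section 7.6, complete response reads "All index lesion(s) must have regressed to normal size". Partial response is a fall of at least 50% in the summed products of the index lesions. Stable disease is whatever is not CR, PR or PD. Progressive disease can also arise from "appearance of any new sites of lymphadenopathy that measure >1.5" cm, which can be judged without a baseline lesion.
- **Index lesions.** Appendix 15.2 sets a maximum of six, with no minimum and no rule for a subject with none.
- **Population.** Under section 8.6, any subject given at least one dose "will be included for all analyses for each Visit they complete". No subset evaluable for nodal response is defined.

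**The concern.** The nodal response proportion should describe what happens to enlarged nodes on sirolimus. A subject with no index lesion has nothing that can shrink, so CR or PR cannot be shown whatever the drug does. If that subject stays in the denominator, the reported rate falls with the share of node-free entrants, and two cohorts with the same nodal effect would report different rates.

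Such entrants are plausible. Section 1.1 says anti-IL-6 blockade improves lymphadenopathy in some patients. Inclusion 3 admits patients who were intolerant of it, and defines relapse by symptoms. Exclusion 2 permits stable or tapering corticosteroids and, for some subjects, anti-IL-6 therapy continuing at entry. How many will enrol cannot be derived from the documents.

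**Working it through.** **1. Can a node-free subject enter?** Inclusion 4 has six items, three of them objective (hemoglobin, weight loss, node).

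- All subsets of six items: 2^6 = 64. Subsets with no objective item: 2^3 = 8. With at least one objective item: 64 − 8 = 56. Removing the 3 that consist of a single objective item leaves 53 permitted patterns.
- Without the node item: 2^5 = 32. With neither hemoglobin nor weight loss: 2^3 = 8. That leaves 24. Removing the 2 single-item patterns leaves 22.

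So 22 of the 53 permitted patterns contain no node. This counts patterns and is not a forecast of how often they occur.

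**2. How does section 7.6 classify such a subject?** Appendix 15.2 gives one worked nodal figure, for the CBR threshold. It reproduces: 3.0 × 2.0 = 6.0, 6.0 × 0.75 = 4.5, and 2 × 2.25 = 4.5. Like the Cheson categories, it starts from a baseline node.

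| Category | Needs a baseline index lesion? | Subject with none |
|---|---|---|
| CR | Yes: lesions must have regressed | Not attainable on a natural reading |
| PR | Yes: 50% fall from baseline sum | Baseline sum is 0; undefined |
| PD | Not for new sites > 1.5 cm | Attainable |
| SD | Residual category | Where the subject falls |

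Section 8.6 then keeps the subject in the denominator.

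**3. Size of the dilution.** Inputs: N = 24 evaluable subjects (section 8.4); nodal response taken as CR or PR; true response r = 1/3 among subjects with nodes (assumed); k node-free subjects (assumed).

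Responders = r × (24 − k). Reported rate = r × (24 − k)/24. Intervals are 95% Clopper-Pearson.

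| k | Responders | Denominator 24 | Denominator 24 − k |
|---|---|---|---|
| 0 | 8 | 8/24 = 33.3% (15.6 to 55.3) | same |
| 3 | 7 | 7/24 = 29.2% (12.6 to 51.1) | 7/21 = 33.3% (14.6 to 57.0) |
| 6 | 6 | 6/24 = 25.0% (9.8 to 46.7) | 6/18 = 33.3% (13.3 to 59.0) |

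The shortfall is r × k/24: 4.2 points at k = 3 and 8.3 points at k = 6. It scales with r. At r = 1/2 and k = 6 the figures are 9/24 = 37.5% (18.8 to 59.4) against 9/18 = 50.0% (26.0 to 74.0).

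**4. Does the same problem reach CBR?** Each of the 22 node-free patterns holds at least two abnormal non-nodal CBR items. A positive CBR needs improvement in only one criterion without disqualifying worsening, so these subjects can be scored positive or negative without a node. Appendix 15.2 does tie the nodal item to a baseline lesion: "The largest of the index lesions selected at baseline should be analyzed to determine CBR response". Because it compares that same node with its baseline, new nodes do not count as CBR worsening for any subject, with or without an index lesion.

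**The case against.** The strongest reply is that nothing is undefined: stable disease is the stated default, and an all-dosed denominator is a conservative convention. The endpoint is secondary, section 8.4 powers nothing on it, and section 8.5.1 names a test only for CBR. The intervals in the table overlap almost entirely. Node-free entrants may also be few, since inclusion 3 selects patients whose disease was not controlled or who could not tolerate therapy, the diagnosis needs nodes in two stations, and the index threshold is only 1.0 × 1.0 cm. Section 10.2 also allows an item to be coded as not applicable, so these subjects could be identified later.

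Most of this stands as a limit on size. It does not remove the point. Conservative counting suits a subject who could have responded and did not; here the outcome cannot occur. The dilution is a shift in the estimate that sampling error neither explains nor corrects. Coding an item as not applicable sets no denominator.

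Two stronger readings are tempting, and the documents do not support them.

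- A reader might infer that a node-free subject is automatically a complete response, because every one of zero lesions is normal. Section 7.6 says the lesions must have regressed, which presupposes a lesion. An inflated rate on that reading should not be claimed.
- A reader might infer that CBR, the primary endpoint, is also mis-scored. It is an any-of composite, and an item normal at baseline simply cannot contribute improvement, just as fever cannot in an afebrile subject. The blind spot for new nodes comes from Appendix 15.2 and applies to everyone. CBR and modified Cheson are separate endpoints, so disagreement between them is not a contradiction.

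**Conclusion.** The point holds for the secondary nodal response proportion only. Inclusion 4 can admit subjects with no index lesion, and the text as written counts them as non-responders. The bias is downward, by r × k/24. With 24 evaluable subjects and a one-third response among those with nodes, that takes 33% to 29% for 3 node-free subjects and to 25% for 6. Both r and k are assumptions; if every subject has a baseline node, the effect is nil. The primary endpoint, the interim rule and the sample size are unaffected. This is a modest gap in pre-specification that is easily closed before the data are seen.

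**What to change.** In sections 8.2 and 8.6, define the denominator for modified Cheson nodal response as dosed subjects with at least one index lesion at baseline, and report the number of dosed subjects without one. Progression by new sites can still be listed for the latter. Leave inclusion 4 as it is.

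As an optional addition, state in section 7.6 or Appendix 15.2 that new nodes do not count as CBR worsening for any subject, and provide a sensitivity listing of CBR-positive subjects who have modified Cheson PD at the same visit. A new-node worsening rule for node-free subjects alone is not advised. It would make the primary endpoint differ by baseline nodal status and would alter an instrument adopted from the siltuximab Phase I study.

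The cost is wording only, since imaging is already scheduled and centrally reviewed. The nodal estimate rests on fewer subjects: at k = 6 the interval is 13.3 to 59.0% on 18 subjects, against 9.8 to 46.7% on 24.

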4.2 Exclusion Criteria

To be eligible, subjects must not violate any of the below exclusion criteria.

- 1. Subjects cannot be pregnant or nursing females
 - Women of childbearing potential must have a negative pregnancy test documented at the Baseline Visit. Subjects of reproductive potential may not participate unless they have agreed, as part of the informed consent, to use an effective contraceptive method for the duration of the study and for at least 12 weeks after ending treatment
- 2. Subjects cannot have received any systemic therapy(ies) intended to treat iMCD other than corticosteroids within 14 days of enrollment
 - Corticosteroid treatment must have been initiated more than 28 days prior to enrollment and be maintained at a stable or tapering dose (prednisone or equivalent up to 1 mg/kg/day) prior to enrollment; dose cannot be elevated for the duration of the study but can be maintained or tapered
 - For subjects who cannot or are unwilling to undergo a 14 day washout period:
 - i. Anti-IL-6 therapy may be permitted if the subject has been on therapy for at least 3 months, no toxicity has been documented, and sufficient disease control is not achieved
 - ii. Anti-IL-6 therapy must be discontinued within the first 6 weeks after starting sirolimus
- 3. Subjects cannot have previously received sirolimus monotherapy to treat iMCD

- 4. Subjects cannot have any of the following:
 - ECOG >3 (or Karnofsky/Lansky score ≤ 60 in children)
 - Estimated glomerular filtration rate (eGFR) < 30 mL/min/1.73 m² or creatinine > 3.0 mg/dL
 - Absolute neutrophil count (ANC) < 1000 x 10⁹/L (< 500 x 10⁹/L in children)
 - Hemoglobin ≤ 6.5 g/dL (transfusion independent, defined as not receiving a red blood cell transfusion for ≥ 7 days prior)
 - Aspartate aminotransferase (AST) or alanine aminotransferase (ALT) laboratory values greater than three times the upper limit of normal
 - Albumin < 2 g/dL (transfusion independent, defined as not receiving intravenous albumin for ≥ 7 days prior)
 - Platelet count $\leq 40 \times 10^9$ /L (transfusion independent, defined as not receiving platelet transfusion for ≥ 7 days prior)
 - Pulmonary involvement or interstitial pneumonitis with dyspnea (adequate pulmonary function is defined as pulse oximetry > 94% on room air if there is clinical indication for determination [e.g. dyspnea at rest, history of interstitial pneumonitis, etc.])
 - Fasting cholesterol > 300 mg/dL or fasting triglyceride > 400 mg/dL
- 5. Subjects cannot have uncontrolled infection or infectious disease(s) that is/are exclusionary for / mimickers of iMCD (**Appendix 15.1**)
 - Fungal disease must be stable for at least two weeks before enrollment
 - Subjects with history of recent bacteremia must have a documented negative blood culture before enrollment
 - Subjects with past history of non-therapy related opportunistic infection should discuss eligibility and possible immunologic evaluation with the licensed site investigator prior to enrollment
- 6. Subjects cannot have rheumatologic disease(s) that is/are exclusionary for / mimickers of iMCD (**Appendix 15.1**)
- 7. Subjects cannot have a prior malignancy except for: (1) adequately treated basal cell or squamous cell skin cancer, (2) in situ cervical cancer, or (3) other cancer for which the subject has not received treatment within one year prior to enrollment
 - Other cancers will only be acceptable if the patient's life expectancy exceeds five years and they are not exclusionary diagnoses for iMCD (**Appendix 15.1**)
- 8. Subjects cannot have a documented history of human immunodeficiency virus (HIV) or HHV-8 infection, or severe combined immunodeficiency syndrome
- 9. Subjects cannot have a history of liver or lung transplantation
- 10. Subjects cannot have ongoing or planned participation in another clinical trial involving iMCD directed treatment or that involves immunomodulatory or anti-neoplastic treatment
- 11. Subjects cannot have prior sensitivity / allergy to any formulation of sirolimus, its components or its analogues
- 12. Subjects cannot have serious medical illness, or psychiatric illness or disorders that could potentially interfere with the completion of treatment according to this protocol or participation in the trial
- 13. Subjects cannot have psychiatric disorders that compromise the ability to provide informed consent
- 14. Subjects cannot have any other condition or finding that in the opinion of the investigator would make participation in this trial inappropriate

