6.6 Subject Withdrawal

The criteria for enrollment must be followed explicitly. If a subject who does not meet enrollment criteria is inadvertently enrolled, that subject should be discontinued from the study. A subject may voluntarily discontinue participation in this study at any time without impact to their care. The licensed site investigator or Lead Principal Investigator may also, at his or her discretion, discontinue the subject from participating in this study at any time. If a subject is prematurely discontinued from participation in the study for any reason, at any time, at either the licensed site investigator's discretion or the subject's request, an effort must be made to document the reason(s) why a subject failed to return to the study site for necessary visits or is discontinued from the study. Subjects withdrawn from the study may be replaced at the Lead Principal Investigator's discretion. The primary reason for discontinuing participation in the study must be stated in the CRF and may include, but is not limited to, one of the following:

- Progressive disease as determined by the licensed site investigator
- Use of unapproved concomitant medications including any systemic therapy(ies) intended to treat iMCD, as described in the eligibility criteria
- Occurrence of intolerable AEs
- Withdrawal of consent by subject
- Noncompliance with protocol, e.g., the subject fails to appear at one or more visits
- Development of an intercurrent illness, injury, or medical condition likely to interfere with subject safety, the overall assessment, or the required administration of study medication
- Pregnancy
- Development of any condition for which the licensed site investigator feels treatment withdrawal is justified
- Termination of the study

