12.1 Risks

The risk to patients of exposure to the treatment intervention, sirolimus, as related to AEs is relatively low. Sirolimus is an FDA-approved therapy with an established safety profile. Although uncommon, AEs are possible and will be monitored by study staff and licensed site investigators. The most common (≥20%) adverse reactions reported for sirolimus 2 mg/day at a higher incidence than reported for placebo include:

- peripheral edema
- hyperlipidemia, hypercholesterolemia, hypertriglyceridemia
- increased creatinine
- constipation
- hypertension
- abdominal pain / diarrhea
- headache
- arthralgia

Other less common serious complications include:

- angioedema
- leucopenia
- thrombocytosis / thrombocytopenia
- fluid accumulation

- impaired wound healing
- proteinuria
- interstitial lung disease/non-infectious pneumonitis
- calcineurin inhibitor-induced hemolytic uremic syndrome/thrombotic thrombocytopenic purpura/thrombotic microangiopathy

The below table summarizes the known adverse events (AEs) categorized based on timing and frequency:

Known Adverse Events (AEs)									
	Common	Occasional	Rare						
	21-100 out of every 100	5-20 out of every 100	<5 out of every 100						
Immediate: 1-2 days of receiving drug	Nausea, vomiting, oral ulcers	Rash	Allergic reaction (may be life threatening)						
Prompt: 2-3 weeks on drug	Increased cholesterol, increased blood pressure, decreased kidney function, diarrhea	Infections, swelling, weight gain, muscle/joint pain, tremor, acne, rash, abdominal pain, mucositis, headache	Decreased red and white blood cells generated in bone marrow, decreased liver function						
Delayed: Any time later during therapy, excluding the above conditions	Acne		Malignancy resulting from this treatment, destruction of red blood cells and decreased kidney function, interstitial lung disease, hemolytic uremic syndrome/thrombotic thrombocytopenic purpura*						
Late: Any time after completion of treatment			Interstitial lung disease						
Sirolimus was embryo/feto toxic in rats at dosages of 0.1 mg/kg and above (approximately 0.2 to 0.5 is the clinical doses adjusted for body surface area). Embryo/feto toxicity was manifested as mortality and reduced fetal weights (with associated delays in skeletal ossification). Sirolimus is excreted in trace amounts in milk of lactating rats. It is not known whether sirolimus is excreted in human milk.									

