15.1 Diagnostic Criteria for iMCD

I. Major Criteria (need both):

Histopathologic lymph node features consistent with the iMCD spectrum (Figure 5). Features along the iMCD spectrum include (need grade 2-3 for either regressive GCs or plasmacytosis at minimum):

Regressed/atrophic/atretic germinal centers, often with expanded mantle zones composed of concentric rings of lymphocytes in an "onion skinning" appearance

Vascularity, often with prominent endothelium in the interfolliduar space and vessels penetrating into the GCs with a "lollipop" appearance

Sheetlike, polytypic plasmacytosis in the interfollicular space

Hyperplastic GCs

2. Enlarged lymph nodes (≥1 cm in short-axis diameter) in ≥2 lymph node stations

II. Minor Criteria (need at least 2 of 11 criteria with at least 1 laboratory criterion)

Laboratory*

- 1. Elevated CRP (>10 mg/L) or ESR (>15 mm/h)†
 - 2. Anemia (hemoglobin <12.5 g/dL for males, hemoglobin <11.5 g/dL for females)
- Thrombocytopenia (platelet count <150 k/μL) or thrombocytosis (platelet count >400 k/μL)
 - 4. Hypoalbuminemia (albumin <3.5 g/dL)
- Renal dysfunction (eGFR <60 mL/min/1.73m²) or proteinuria (total protein 150 mg/24 h or 10 mg/100 ml)
 - Polyclonal hypergammaglobulinemia (total γ globulin or immunoglobulin G > 1700 mg/dL)

Clinical

- 1. Constitutional symptoms: night sweats, fever (>38°C), weight loss, or fatigue (≥2 CTCAE lymphoma score for B-symptoms)
- 2. Large spleen and/or liver
 - 3. Fluid accumulation: edema, anasarca, ascites, or pleural effusion
- 4. Eruptive cherry hemangiomatosis or violaceous papules
 - 5. Lymphocytic interstitial pneumonitis

III. Exclusion Criteria (must rule out each of these diseases that can mimic iMCD)

Infection-related disorders

- 1. HHV-8 (infection can be documented by blood PCR, diagnosis of HHV-8-associated MCD requires positive LANA-1 staining by IHC, which excludes iMCD)
 - 2. Clinical EBV-lymphoproliferative disorders such as infectious mononucleosis or chronic active EBV (detectable EBV viral load not necessarily exclusionary)
- 3. Inflammation and adenopathy caused by other uncontrolled infections (eg, acute or uncontrolled CMV, toxoplasmosis, HIV, active tuberculosis)

Autoimmune/autoinflammatory diseases (requires full clinical criteria, detection of autoimmune antibodies alone is not exclusionary)

- 1. Systemic lupus erythematosus
- 2. Rheumatoid arthritis
- 3. Adult-onset Still disease
 - 4. Juvenile idiopathic arthritis

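### The neutrophil exclusion limits in Section 4.2 equal 1,000,000 and 500,000 cells/µL as written, which no candidate could meet; the number or the unit needs correcting

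*Combined protocol and SAP*

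**What the plan says.** Section 4.2 opens its list strictly: "To be eligible, subjects must not violate any of the below exclusion criteria". Exclusion 4 then groups the laboratory and organ-function limits under "Subjects cannot have any of the following". The neutrophil entry reads "Absolute neutrophil count (ANC) < 1000 x 10⁹/L", with "< 500 x 10⁹/L in children" in brackets. Four entries further down, the platelet exclusion is at or below 40 x 10⁹/L.

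Appendix 15.1 gives platelet cut-offs in thousands per µL: the lower begins "Thrombocytopenia (platelet count <150 k" per µL, and the upper is 400 k/µL. Appendix 15.4 names ANC as part of the blood count, with no unit and no limit. The neutrophil limit is not restated anywhere else in the document.

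Section 6.6 adds "The criteria for enrollment must be followed explicitly", followed by "If a subject who does not meet enrollment criteria is inadvertently enrolled, that subject should be discontinued from the study".

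**The concern.** The exclusion works downwards: a count below the limit makes the subject ineligible. A limit set far too high therefore excludes everyone instead of only those with low counts. On the written scale the adult and child limits lie above any count a candidate could plausibly have, so the criterion cannot separate eligible from ineligible subjects.

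Two things are at stake. The first is the safety screen. Section 12.1 lists "Decreased red and white blood cells generated in bone marrow" among the known effects of sirolimus (in the rare column, under 5 in 100) and names leucopenia among the less common serious complications, so the baseline neutrophil limit has a purpose. The second is consistency across up to four sites. Anyone who applies a workable limit is applying one that the protocol does not contain, although Section 6.6 asks for explicit adherence.

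**Working it through.** **Inputs, all from the protocol**
- Adult ANC limit: 1000 x 10⁹/L (Section 4.2, exclusion 4)
- Child ANC limit: 500 x 10⁹/L (same line)
- Platelet exclusion: 40 x 10⁹/L (same list)
- Platelet cut-offs: 150 and 400 k/µL (Appendix 15.1)

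**Conversion.** 1 L = 10⁶ µL, so X x 10⁹/L = X x 10⁹ / 10⁶ = X x 1000 cells/µL.

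| Limit | As written | Per µL |
|---|---|---|
| ANC, adults | 1000 x 10⁹/L | 1,000,000 |
| ANC, children | 500 x 10⁹/L | 500,000 |
| Platelet exclusion | 40 x 10⁹/L | 40,000 |
| Platelet cut-offs, 15.1 | 150 and 400 k/µL (= 150 and 400 x 10⁹/L) | 150,000 and 400,000 |

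**Internal comparison.** The platelet exclusion in 4.2 sits on the same scale as the cut-offs in 15.1: 40 against 150 and 400, all in 10⁹/L. The ANC limits are 1000/40 = 25 times (adults) and 500/40 = 12.5 times (children) the platelet exclusion. This comparison shows how the protocol uses the unit. It does not show which neutrophil counts are possible.

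**Who is excluded on a literal reading.** The documents give no range of baseline ANC, so I assume one that is deliberately too wide: 0.5 to 400 x 10⁹/L, or 500 to 400,000/µL. Its upper end, 400, is below both 500 and 1000, so every value in the range is excluded under both the adult and the child limit.

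**Size of the error, under an assumption.** Suppose the numerals 1000 and 500 were meant per µL. Then:
- 1000/µL x 10⁶ µL/L = 10⁹/L = 1.0 x 10⁹/L, and 1000 / 1.0 = 1000
- 500/µL x 10⁶ µL/L = 0.5 x 10⁹/L, and 500 / 0.5 = 1000

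On that assumption both written limits are too high by a factor of 1000. These conversions measure the discrepancy and are not proposed limits.

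**Sensitivity to a misread character.** If the source document has an exponent of 6, then 1000 x 10⁶/L = 1000/µL and 500 x 10⁶/L = 500/µL, and there is no error.

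**The case against.** **The exponent may have been misread.** The text was extracted from PDF, a superscript 6 and 9 look alike, and there are character errors elsewhere in the extraction. The doubt is fair, and it is the reason to check the source first. It remains small, because the 9 appears in both the adult and the child limit and the misread would have had to happen twice.

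**The slip is obvious and harmless.** A literal reading empties a trial that plans to enrol up to 40 subjects, so any investigator would notice it. Eligibility is judged by the site investigator and confirmed centrally by the Lead Principal Investigator (Sections 3.1 and 3.1.1), which limits divergence between sites. Most of this stands. Sites would probably read the limits per µL, and no endpoint, sample size, interim rule or analysis depends on them. It does not make the written criterion right, and there is no correct statement elsewhere to fall back on.

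**Stronger readings that the documents do not support**
- A reader might infer that every enrolled subject must be withdrawn. Section 6.6 says such a subject should be discontinued, and it speaks of inadvertent enrolment. It is not a mandate to empty the trial.
- A reader might infer that the data checks or audits are wrong too. Section 10.2 describes general logical checks for mis-entry and mentions no ANC check. Section 11.1 provides for eligibility review, so a nominal discrepancy could arise, but no more than that is shown.
- A reader might take the factor of 1000, or the unit as the place of the error, as established. The intended limits are not stated, so the slip could lie in the numeral, the exponent or the unit.

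**Conclusion.** The point holds as an error in a written eligibility and safety threshold. As printed, the limits are 1,000,000/µL for adults and 500,000/µL for children, and they do not fit the scale on which the same list states its platelet limit. Read literally, the criterion excludes every candidate whose count lies anywhere in the very wide range assumed above. The factor of 1000 holds if the numerals were meant per µL, which is likely but not stated. All of this assumes that the extracted exponent is faithful to the source.

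The statistical effect is small. The error does not show that anyone was wrongly enrolled or excluded, and it does not undermine the efficacy analysis. It merits correction because the criterion screens for a known risk of the drug, the protocol asks for explicit adherence, and no other section supplies the right figure.

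**What to change.** 1. Check the ANC line in Section 4.2 against the source document, looking at the exponent in both limits.
2. If the text is as extracted, have the sponsor confirm the intended adult and child limits. This review proposes neither.
3. Correct the number or the unit of both limits, so that they are on the same scale as the platelet entry in that list.
4. Make the Patient Evaluation Form, and any data check that uses the limit, match the corrected text.
5. Notify the sites.

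The cost is one corrected line, a check of any form that uses it, and a notice to sites. No sample size, endpoint or analysis changes.
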